### **9.4. Pharmacokinetic Analysis**

The plasma SNF472 PK parameter, Cmax, will be calculated, individual and mean.

### **9.5. Determination of Sample Size**

Based on recent historical data from a U.S. large dialysis provider organization, approximately 25% of calciphylaxis skin lesions are considered to be improved over a 3-6 month period (data unpublished; personal communication). A total of 15 subjects who complete 12-week of treatment was determined necessary to show with 80% power that the percentage of subjects for which the primary ulcer is totally or partially healed after 12 weeks of treatment is greater than 25%. For these calculations, it was assumed that the percentage of totally or partially healed subjects for SNF472 will be 60%.

## **10. ETHICAL, LEGAL, AND ADMINISTRATIVE ASPECTS**

### **10.1. Data Quality Assurance**

The Sponsor or designee will conduct Clinical Unit visits to, inspect the facilities, and to ensure that all the clinical study procedures are followed as per protocol.

The Investigator must prepare and maintain adequate and accurate case histories designed to record all observations and other data pertinent to the clinical trial for each clinical trial patient. All information recorded in the CRF for this clinical trial must be consistent with the patient's source documentation.

### **10.2. Data Collection**

Paper CRFs will be distributed to the clinical sites. Once the CRFs are source data verified, the originals are sent to the sponsor. The sponsor digitizes the CRFs for data entry. The data from the digitized CRFs will be entered into a database using [REDACTED]

Once the original CRFs are sent to the sponsor, all data additions, changes or corrections will be captured on the query reports.

The responsible Clinical Monitor will check source data during the monitoring visits to the Clinical Unit. The Investigator will ensure that the data collected are accurate, complete and legible.

All clinical work conducted under this Clinical trial Protocol will follow Good Clinical Practice (GCP) principles [54].

### **10.3. Source Documents**

All data obtained during the clinical trial should be promptly recorded in the CRF, as is described in section 10.2.

The CRF entries for each patient will be checked against source documents by the monitor. Instances of missing or uninterpretable data will be discussed with the Investigator for resolution.

### **10.4. Access to Source Documents**

During the course of the clinical trial, a Monitor will make Clinical Unit visits to review Clinical Trial Protocol compliance, assess IMP accountability and ensure that the clinical trial is being conducted according to pertinent regulatory requirements. CRF entries will be verified against source documents. The review of medical records will be handled confidentially to ensure clinical trial patient anonymity.

Checking of CRF entries for completeness and clarity and verifying with source documents, will be required to monitor the clinical trial for compliance with GCP and other regulations. Moreover, Regulatory Authorities of certain countries and ECs/IRBs may wish to carry out source data inspections on-site, and the Sponsor's Clinical Quality Assurance

Group may wish to carry out audits. Direct access to source data will be required for these inspections and audits; they will be carried out giving due consideration to data protection and patient confidentiality. The Investigator assures the Sponsor of the necessary support at all times.

#### **10.5. Data Management**

[REDACTED]

A data management plan (DMP) will describe the work- and data-flow within this clinical trial. Versions for the computer systems and the coding will be defined in the DMP.

#### **10.6. Archiving Clinical Trial Documents**

According to International Conference on Harmonisation (ICH) guidelines, essential documents should be retained for a minimum of 2 years after the last approval of a marketing application in an ICH region and until there are no pending or contemplated marketing applications in an ICH region or at least 2 years have elapsed since the formal discontinuation of clinical development of the IMP. However, these documents should be retained for a longer period if required by the applicable legal requirements.

#### **10.7. Good Clinical Practice**

The procedures set out in this Clinical trial Protocol are designed to ensure that the Sponsor and the Investigator abide by the principles of the ICH guidelines on GCP[54], and the Declaration of Helsinki (Version 1996)[55]. The clinical trial will also be carried out in keeping with national and local legal requirements.

#### **10.8. Informed Consent**

Before each patient is enrolled in the clinical trial, written informed consent will be obtained from the patient according to the local regulatory and legal requirements. The Patient Information Sheet and ICF must be signed and dated; one copy will be handed to the patient and the Investigator will retain a copy as part of the clinical trial records. The Investigator will not undertake any investigation specifically required for the clinical trial until written consent has been obtained. The terms of the consent and when it was obtained must also be documented in the CRF.

The Investigator must ensure that the patient is given full and adequate oral and written information about the nature, purpose, possible risk and benefit of the clinical trial. Patients must also be notified that they are free to withdraw from the clinical trial at any time without prejudice to future care. The patient should be given the opportunity to ask questions and allowed time to consider the information provided.

If a Clinical Trial Protocol Amendment is required, the Patient Information Sheet and ICF may need to be revised to reflect the changes to the Clinical Trial Protocol. If the Patient Information Sheet and ICF are revised, they must be

reviewed and approved by the responsible EC/IRB, and signed by all patients subsequently enrolled in the clinical trial as well as those currently enrolled in the clinical trial.

#### **10.9. Protocol Approval and Amendment(s)**

Before the start of the clinical trial, the Clinical Trial Protocol and other relevant documents will be approved by the EC/IRB/Regulatory Authorities in accordance with local legal requirements. The Sponsor must ensure that all ethical and legal requirements have been met before the first patient is enrolled in the clinical trial.

This Clinical Trial Protocol should be followed exactly. To alter the Clinical Trial Protocol, amendments must be written, which must be released by the responsible staff and receive EC/IRB/Regulatory Authority approval prior to implementation (as appropriate).

Administrative changes may be made without the need for a substantial Clinical Trial Protocol Amendment, but will also be mentioned in the integrated Clinical Study Report. All Clinical Trial Protocol Amendments will be distributed to all Clinical Trial Protocol recipients, with appropriate instructions.

#### **10.10. Duration of the Clinical trial**

The maximum expected duration of participation for an individual patient, including Screening and Follow-up, will be approximately 15 weeks.

#### **10.11. Confidentiality Data Protection**

All clinical trial findings and documents will be regarded as confidential. The Investigator and members of his research team must not disclose such information without prior written approval from the Sponsor. The Investigator shall permit access to subject's records and source documents for the purpose of monitoring, auditing or inspection by Sanifit, authorized representatives of Sanifit, regulatory authorities and IRB/IEC's only.

The anonymity of participating patients must be maintained. Patients will be specified on documents by their patient number, initial or birth date, not by name. Documents that identify the patient (e.g., the signed Patient Information Sheet and ICF) must be maintained in confidence by the Investigator.

#### **10.12. Other Ethical and Regulatory Issues**

If a safety issue of clinical relevance is identified, from review of any data, then the Sponsor will issue prompt notification to all parties – Investigator and EC/IRB/Regulatory Authorities.

A safety issue of clinical relevance is one that has a relevant impact on the course of the clinical trial or program (including the potential for suspension of the clinical trial program or amendments to the Clinical Trial Protocol) or warrants immediate update of the Patient Information Sheet and ICF.

### 10.13. Liability and Insurance

The Sponsor will take out reasonable third party liability insurance cover in accordance with all participating countries (Spain, UK, and USA) legal requirements. The civil liability of the Investigator, the persons instructed by him and the hospital, practice or institute in which they are employed and the liability of the Sponsor with respect to financial loss due to personal injury and other damage that may arise as a result of the carrying out of this clinical trial are governed by the applicable laws and GCP guidelines.

The Sponsor will arrange for patients participating in this clinical trial to be insured against financial loss due to personal injury caused by the pharmaceutical products being tested or by medical steps taken in the course of the clinical trial.

The method and manner of compensation to patients should comply with applicable regulatory requirement(s).

### 10.14. Publication Policy

The sponsor recognizes the fundamental obligation of the institution for publication of nature, purpose and result of the work performed.

With regard to a publication about the substance SNF472 the Institution, upon Sponsor's previous written consent, shall have the right to publish or present the results of the Study conducted under this Agreement, including Study Data after providing a copy of the proposed publication to the Sponsor at least thirty (30) days prior to submission for publication or disclosure and at least ten (10) days prior to submission for Abstracts. If the Sponsor believes that the manuscript contains any of its Confidential Information or subject matter that is patentable or otherwise protected by IP rights, the sponsor can exceptionally demand a delay of the publication to maximum 90 days after submission of the manuscript, if this is necessary for the protection of intellectual property. The notification will include specific details to be amended from the manuscript in mutual understanding. The approval shall not be unreasonably denied and the scientific content may not be changed. If no objection is received in writing within the above mentioned period, the Party seeking disclosure will be free to publish the manuscript or other form of disclosure as submitted to the Sponsor.

The Sponsor retains the right to nominate authors in any publication at its sole discretion, provided they contributed in the conception, design, execution, follow-up and/or discussion of results of the study.

The Institution shall grant, and shall cause the Coordinating Investigator and the German Principle Investigators to grant, the Sponsor a worldwide, royalty-free, non-exclusive license to reproduce and distribute copies of any Publication relating to the Study in which the Institution, the Principal Investigator, or any other Study Staff member retains the

copyright. The Institution will publicly acknowledge in each Publication the Sponsor's contribution as follows: "Data used in preparation of this manuscript were obtained with support of Laboratoris Sanifit (plus Address)".

The institution can publish all data which are collected regardless of the substance SNF472 (for example, but not finally: Calciphylaxis Foreground, Imaging systems or methods etc.) without prior submission and approval by the sponsor.

2. LIST OF ABBREVIATIONS AND DEFINITION OF TERMS

AE	Adverse event
BWAT	Bates Jensen Wound Assessment Tool
C _{max}	Maximum observed plasma concentration
CS	Clinically significant
CUA	Calciphic Uremic Arteriopathy
CRF	Case Report Form
ECG	Electrocardiogram
EOS	End of Study
FU	Follow-Up
ICF	Informed Consent Form
ICH	International Council on Harmonisation
IMP	Investigational medicinal product
IV	Intravenous
N	Number of subjects
NSAID	non-steroidal anti-inflammatory drugs
L	Litre
PK	Pharmacokinetic(s)
PTH	Parathyroid Hormone
QT	QT interval
QTc	Corrected QT interval
QTcB	Corrected QT interval using Bazett's formula
QTcF	Corrected QT interval using Fridericia's formula
SAE	Serious adverse event
SAP	Statistical Analysis Plan
SCR	Screening
SOC	System Organ Class
VAS	Visual analog scale

4. INTRODUCTION

This document describes the statistical methods and data presentations to be used in summarizing and analyzing the data for Protocol SNFCT2015-04. Background information is provided for the overall study design and objectives. The reader is referred to the study protocol and case report forms (CRFs) for details of study conduct and data collection.

5. STUDY OBJECTIVES AND ENDPOINTS

5.1 Study objectives

The objective of this study is to evaluate the safety and efficacy of SNF472 on top of standard of care on promoting wound healing and other parameters of therapeutic response in haemodialysis subjects with calciphylaxis (calcific uraemic arteriopathy, CUA).

5.2 Endpoints

5.2.1 Primary endpoint

- The primary endpoint is the absolute change in BWAT total score between baseline (Week 1) and Week 12 for the primary lesion (the largest one).

5.2.2 Secondary endpoints

Wound healing:

- Absolute change from baseline in BWAT total and component scores by visit for the primary lesion, secondary lesion, and tertiary lesions.
- Qualitative change from baseline in imaging score by visit for the primary lesion, secondary lesion, and tertiary lesions.

Pain:

- Absolute change from baseline by visit in the Pain Visual Analog Scale (VAS).

Quality of Life:

- Absolute change from baseline at Weeks 6 and 12 in global score and subscales of wound QoL score.

Wound and disease complications:

- Presence/absence of new wound infection at any time post baseline
- Presence/absence of new systemic infection at any time post baseline
- Surgical treatment of the wound at any time post baseline
- Requires or prolongs hospitalization
- Death

6. STUDY DESIGN

6.1 General study design and plan

It is an open-label single-arm clinical trial. Up to 15 CUA subjects will be enrolled, treated, and followed over a 12-week period to assess the safety and efficacy of SNF472 for the treatment of CUA.

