### 5.1. Number of Patients

It is planned to include 15 male or female CUA patients who complete the 12-week treatment period.

Patients who leave the clinical trial before being entered into the study will be considered as screening failures and will always be replaced. Therefore, sufficient reserve patients should be recruited, where possible. Patients withdrawn after dosing may be replaced as needed to obtain 15 patients who complete the 12-week treatment period.

See Section 9.5 for a discussion of sample size.

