6.4 Sample size

Given the exploratory purpose of the study, the sample size will not be recalculated.

The original sample size justification was:

Based on recent historical data from a U.S. large dialysis provider organization, approximately 25% of calciphylaxis skin lesions are considered to be improved over a 3-6-month period (data unpublished; personal communication). A total of 15 subjects was determined necessary to show with 80% power that the percentage of subjects for which the primary ulcer is totally or partially healed after 12 weeks of treatment is greater than 25%. For these calculations, it was assumed that the percentage of totally or partially healed subjects for SNF472 will be 60%.

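### The protocol's 15 counts patients who complete 12 weeks; the SAP caps enrolment at 15, repeats the 80% power without the completer condition, and records neither change.

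*SAP*

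**What the plan says.** **Protocol.** The synopsis and sections 4.1, 5.1 and 9.5 all define the sample size by completion of the 12-week treatment period. Section 9.5 reads "A total of 15 subjects who complete 12-week of treatment was determined necessary to show with 80% power". Section 5.1 adds a way to reach the number: "Patients withdrawn after dosing may be replaced as needed to obtain 15 patients who complete the 12-week treatment period". Section 5.5 leaves replacement of withdrawn patients to the discretion of the sponsor and the principal investigator.

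**SAP.** Section 6.1 describes the design as "Up to 15 CUA subjects will be enrolled, treated, and followed over a 12-week period". Section 6.4 opens with "Given the exploratory purpose of the study, the sample size will not be recalculated". It then introduces the protocol's paragraph with "The original sample size justification was", but the key sentence now reads "A total of 15 subjects was determined necessary to show with 80% power". The words that restrict the 15 to completers are gone; the rest of the paragraph is nearly verbatim. Section 10 (changes from the protocol) covers the endpoint analyses, pain medication, withdrawal criteria and efficacy sets. It mentions neither the enrolment limit nor the altered justification.

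**The concern.** In the protocol, 15 is a target for completers. In SAP 6.1 it is a ceiling on enrolment. The two agree only if nobody fails to complete. Once one patient dies or withdraws, the protocol's target cannot be met within the SAP's limit.

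Because SAP 6.4 calls its text the original, someone reading only the SAP would conclude that 15 enrolled patients were always meant to give 80% power. Two things are at stake: when enrolment ends, and whether the quoted power belongs to the trial the SAP describes. Losses are foreseeable, since Protocol 2.2 cites a 1-year survival of 45% in this disease.

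**Working it through.** **Inputs from the documents.** Null rate 25% ("approximately 25% of calciphylaxis skin lesions are considered to be improved over a 3-6 month period"), alternative 60%, n = 15, stated power 80% (Protocol 9.5). One-year survival 45% (Protocol 2.2).

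**Inputs not in the documents, so assumed.** Alpha: one-sided 5% or one-sided 2.5%. Non-completion over 12 weeks: 10–30%. Completion is taken as independent of healing.

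**Step 1: reproduce the plan's figure.** Exact binomial test, n = 15, smallest critical count r with P(X ≥ r | 0.25) ≤ alpha.
- r = 8 at either alpha: P(X ≥ 8 | 15, 0.25) = 0.0173.
- Power = P(X ≥ 8 | 15, 0.60) = 0.787.

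This agrees with the stated 80% to within 2 points. The calculation is sound, provided that all 15 have an outcome.

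**Step 2: a reference loss rate.** At a constant hazard, 12-week survival = 0.45^(12/52) = 0.832, so about 17% are lost to death alone.
- Expected survivors among 15: 15 × 0.832 = 12.5.
- Chance that all 15 survive: 0.832^15 ≈ 6%.
- Enrolment needed to expect 15 completers: 15/0.832 = 18.04, so 19.

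**Step 3: power with 15 enrolled and no replacement.** The number of completers M is Binomial(15, 1 − d), where d is the non-completion rate. For each M the exact test is redone at that size, and power is averaged over M. The last column keeps the 8-of-15 rule and counts non-completers as not healed, so the success rate is 0.60 × (1 − d).

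| d | Expected completers | Power among completers, one-sided 5% | Same, one-sided 2.5% | Non-completers not healed |
|---|---|---|---|---|
| 0 | 15 | 78.7% | 78.7% | 78.7% |
| 10% | 13.5 | 78.6% | 72.1% | 62% |
| 17% | 12.5 | about 75% | about 68% | about 50% |
| 20% | 12.0 | 73.3% | 65.6% | 44% |
| 30% | 10.5 | 68.7% | 57.1% | 26% |

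**Step 4: why one value of n misleads.** Exact power is saw-toothed because the critical count is an integer. At one-sided 5% it is 75.4% at n = 11, 66.5% at 12, 77.1% at 13, 85.0% at 14 and 78.7% at 15. A figure read at n = 12 sits in a trough, so the average over M is the fairer summary.

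**The case against.** The best defence has four parts.

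- **The SAP may only be summarising loosely.** SAP section 4 treats design as background and sends the reader to the protocol for study conduct. The words up to also fit SAP 7.1, where an interim look decides whether enrolment continues. This makes an oversight plausible, but it does not reconcile the two counts.
- **The SAP partly discloses the shift.** It says that the sample size is not recalculated, and sections 8.2.3 and 10 record new efficacy sets, of which the intention-to-treat set does not require completion. That discloses who is analysed. It does not disclose that the 15 in the power statement now counts something else.
- **Replacement is permissive.** A reader might infer that the protocol commits to replacing patients until 15 complete and that the SAP forbids it. Neither follows: Protocol 5.1 and 5.5 allow replacement at discretion, and the SAP is silent on it. What is firm is the completer target on one side and the enrolment limit on the other.
- **The power loss is uncertain.** This stands. Neither document gives an alpha or a loss rate. The 17% rests on a constant hazard, while Protocol 2.2 describes excess mortality concentrated in the first months, and exclusion 4 removes patients not expected to survive beyond 6 months. These push in opposite directions.

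**Conclusion.** The inconsistency is real and rests on the text alone: the SAP attaches 80% power to 15 enrolled patients, whereas the protocol attached it to 15 completers, and the change is not declared. The number 15 itself is not miscalculated.

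The size of the consequence is a range under assumptions. For 10–30% non-completion without replacement, average power among completers is about 79–69% (one-sided 5%) or 72–57% (one-sided 2.5%). At 10% loss and one-sided 5% almost nothing is lost. The loss is much larger if non-completers count as not healed: 62% down to 26%, and about 50% at 17%.

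Two stronger readings are tempting and should not be drawn. One is that power falls to about 67%; that is the value at exactly 12 completers, a low point of the saw-tooth. The other is that the SAP's primary analysis is underpowered by these amounts. That analysis is a paired t-test on BWAT change with multiple imputation in the intention-to-treat set. The documents give no effect size or SD for it, so its power cannot be computed, and the figures here apply only to the healed proportion.

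**What to change.** 1. State once, identically in Protocol 5.1 and 9.5 and SAP 6.1 and 6.4, whether 15 means enrolled or completed and whether withdrawn patients may be replaced.
2. Restore the completer condition in SAP 6.4, so that the text called original matches Protocol 9.5.
3. List any change of count or of replacement in SAP section 10.
4. If the limit of 15 enrolled stands, say in SAP 6.4 that the 80% applied to 15 completers on the healed-proportion endpoint and is not claimed for 15 enrolled. Give the range above with its alpha and non-completion assumptions, not a single figure.
5. If the completer target stands, remove the limit from SAP 6.1 and note that about 19 enrolled would be needed to expect 15 completers at 17% loss.

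With the limit kept, the cost is SAP wording and a protocol clarification, and the power statement becomes less favourable. Keeping the completer target may cost a few extra patients in a population the SAP already describes as hard to find.

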6.2 Visits schedule

Table 001 Visits Schedule

	SCR	TREATMENT PERIOD																											FU									
Week	-2, -1	1			2			3			4			5			6			7			8			9			10			11			12			13
Day		1	3	5	1	3	5	1	3	5	1	3	5	1	3	5	1	3	5	1	3	5	1	3	5	1	3	5	1	3	5	1	3	5	1	3	5	
Informed Consent	X																																					
Demographics	X																																					
Lesions Overview	X																																					
Images Collection	X	X			X						X						X						X													X	X	
Visit	X	X	X	X	X	X	X	X	X	X	X	X	X	X	X	X	X	X	X	X	X	X	X	X	X	X	X	X	X	X	X	X	X	X	X	X	X	
Body Weight	X																X																			X		
Biopsy (if performed by site) ¹	X																																					
Physical Examination	X																																					X
ECG	X																																					X
ECG (pre dose & end of infusion)		X															X																			X		
Safety Laboratory Assessments ²	X	X															X																			X	X	
PTH		X																																			X	
Potassium, Magnesium, Iron (ferritin/transferrin) and Zinc	X																																					X
Potassium, Magnesium, Iron (ferritin/transferrin) and Zinc (predose & end of infusion)*		X																																			X	
Ionised Calcium	X																																					X

¹ Biopsy is not an inclusion criterion, but if performed the report and analysis will be documented

² These data sets will be used from the routine monthly blood analysis performed on each patient

	SCR	TREATMENT PERIOD																																				FU																				
Week	-2, -1	1			2			3			4			5			6			7			8			9			10			11			12			13																				
Day		1	3	5	1	3	5	1	3	5	1	3	5	1	3	5	1	3	5	1	3	5	1	3	5	1	3	5	1	3	5	1	3	5	1	3	5	1	3	5																		
Ionised Calcium (predose & end of infusion)		X			X						X						X						X						X						X						X			X														
Pregnancy Test ³	X										X															X																					X											
Treatment History (prior medication) ⁴	X																																																									
Medical History	X																																																									
Eligibility ⁵	X																																																									
CUA Diagnosis	X																																																									
Treatment (Intravenous SNF472) ⁶		X	X	X	X	X	X	X	X	X	X	X	X	X	X	X	X	X	X	X	X	X	X	X	X	X	X	X	X	X	X	X	X	X	X	X	X	X	X	X	X	X	X	X	X	X	X	X	X									
Wound QoL Score		X															X																																									
Pain Score (VAS scale)	X	X			X						X						X						X						X																		X	X										
Lesion Score (BJWAT)		X			X						X						X						X						X																		X	X										
Biomarkers		X																																																			X					
Plasma PK and PD sampling (predose & end of infusion)*		X																																																X	X							
Concomitant Medication		X	X	X	X	X	X	X	X	X	X	X	X	X	X	X	X	X	X	X	X	X	X	X	X	X	X	X	X	X	X	X	X	X	X	X	X	X	X	X	X	X	X	X	X	X	X	X	X	X	X	X	X	X	X			
Adverse Events		X	X	X	X	X	X	X	X	X	X	X	X	X	X	X	X	X	X	X	X	X	X	X	X	X	X	X	X	X	X	X	X	X	X	X	X	X	X	X	X	X	X	X	X	X	X	X	X	X	X	X	X	X	X			
End of Study Visit																																																								X		

³ Pregnancy test is to be serum at baseline and urine monthly thereafter

⁴ Prior medication includes medications within 6 months of study start

⁵ The inclusion/exclusion criteria will be assessed for each patient at Screening – final entry into the study depends on confirmation by the PI, [name]

⁶ A Treatment Period includes 3 dialysis sessions/week x 12 weeks (36 treatments)

